7.0 CORRELATIVE ANALYSIS

7.1 Overview

Peripheral blood will be obtained for mRNA, DNA, and flow cytometry analyses. While specific details of the processing, extraction, and analysis are included in this protocol, these details may change with innovations in laboratory techniques and hence are considered general guidelines only.

7.2 Correlative Analysis Procedures

Patients enrolled will have peripheral blood collected for analysis before therapy initiation. Patients who have started on chemotherapy (within 30 days) will not have correlative analysis performed. Peripheral blood will be obtained and separated for serum and PBMC analysis. Peripheral blood will be obtained in EDTA coated tubes and CD3+ T-cells isolated using RosetteSep Reagents. We developed a custom Nanostring Codeset, OSU_Senescence, to comprehensively assess the phenotypes of human PBTLs. The OSU_Senescence platform measures *p16* and 70+ additional transcripts indicative of immunosenescence, cell cycle/cellular senescence, T-cell subtype, exhaustion and cytokine production. Examples of OSU_Senescence detectors include T-cell subtypes (e.g. *TBX21/TH1*, *GATA3/TH2*, *FOXP3/Treg*), immunosenescence (e.g. *CD27*, *CD28*); exhaustion markers (e.g. *PRDM1/Blimp-1*, *PDCD1/PD-*

1, CD274/PDL-1) and standard housekeeping genes. The ability of OSU_Senescence to report dynamic changes in T-cell subtype is a major advantage over traditional real-time PCR-based methods to detect *p16*. Moreover, OSU_Senescence is more cost effective, focused and analytically straightforward than RNA-seq. To increase the power of our Codeset, we developed and tested a companion flow cytometry-based immunophenotyping assay, which can be used to isolate specific T-cell subtypes for downstream functional assays. In addition, we have consulted with Zymo Research Corp. to concurrently analyze changes in the Horvarth⁴⁵ epigenetic clock/DNAge of these cells and PBMCs providing further insight into the global, molecular changes that accompany *p16* expression in PBTLs. All of these studies can be completed from a single, 20 mL sample of human peripheral blood. DNAge and OSU_Senescence mRNA expression will be compared to an age-matched control database developed at OSU.

Patients enrolled have peripheral blood collected for OSU_Senescence analysis serially at Visit 1 (Baseline) and Visit 4 (End of Treatment). Peripheral blood will be obtained in EDTA coated tubes and 10 mL used to isolate CD3+ T-cells using RosetteSep Reagents. At the same time, PBMCs will be isolated from 10 mL of peripheral blood using standard density gradient centrifugation procedures. PBMCs will be cryopreserved in media containing 10% DMSO for future flow cytometric and/or senescence evaluation. RNA and DNA will be extracted from purified PBTL or PBMCs using a column-based commercial nucleic acid kit. Measurement of OSU_Senescence transcripts will then be performed in accordance with standard Nanostring protocols and may be validated by RNA reverse-transcription followed by quantitative real-time PCR. DNA from T-cells and/or PBMCs will be sent to Zymo for DNAge analysis. Levels of OSU_Senescence mRNA expression or DNAge values will be compared to an age-matched control dataset. PBMCs will also be analyzed by flow cytometry to allow for simultaneous multiparametric analysis of cellular markers. Markers of cellular senescence, exhaustion and T-cell regulation will be analyzed.

7.3 Statistical Considerations

Pearson correlations and Spearman correlations will be used to explore the strength of the relationship between *p16*, senescence transcripts, and quantitative prognostic factors (e.g., age). Two-sided hypothesis tests of the correlations will be used to determine if there is evidence of an association between variables. With such a small sample size, this is an exploratory aim. One-way ANOVA and the Tukey-Kramer multiple comparison procedure⁴⁶ will be used to compare levels OSU_Senescence transcripts across the levels of categorical prognostic variables (e.g. stage of disease).

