4.12 Biomarkers

Peripheral blood and stool samples will be collected at baseline prior to treatment and pre and post PT + PMR session. Thereafter, blood will be collected every 6 weeks pre and post PT + PMR session and at additional triggered time points for correlative biomarker studies. Each patient will have a minimum of 6 research blood draws performed (2 pre-treatment) and 4 total post-treatment. The post-PT +PMR blood sample will be drawn from the peripheral IV so an additional needle stick is not required. The blood will be processed into peripheral blood T lymphocytes (PBTLs), plasma, and serum for cellular senescence correlative analyses. The analysis consists of routine laboratory values including hematologic functions, renal function, hepatic function and calculated creatinine clearance, and markers of inflammation and coagulation, and potential molecular markers of aging (P16^{INK4a} Expression, DNAge). The details of this biological assessment are below:

Table 2: Biomarker Assessment

Laboratory Values captured in Routine Practice	Biologic Correlates*
Hematologic functions: WBC HGB Platelets Absolute Neutrophil count Absolute Lymphocyte count Absolute Lymphocyte count	Molecular markers of aging: OSU_Senescence DNAge Inflammatory Cytokines Peripheral blood T Lymphocyte subtyping
Renal Function: BUN Creatinine	
Hepatic function: AST ALT Total Bilirubin Alkaline Phosphatase Albumin	

*patients who have already begun treatment prior to visit 1 will not partake in research blood samples in order to preserve the integrity of the data.

Stool samples will be used for microbiome correlative analyses. At their clinic visit patients will be given a home microbiome collection kit that includes instructions for collecting a sample within 24 hours of their next clinic visit. (Please see **APPENDIX L** for the instructions included in this box.) Briefly, a rigid plastic scaffold is placed over the toilet seat to collect stool in a plastic tub. Patients return the sample at their next clinic. Staff transfer the samples to the [name] lab (IBC 2018R00000115) where stool is transferred to cryo-vials and stored at -80C until processing in batch.

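### Section 7.3 compares ageing-related transcripts across stage and other observed groups with no age term, so for transcripts that track age a stage difference and an age difference cannot be told apart

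*Combined protocol and SAP*

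**What the plan says.** For categorical factors, section 7.3 names "One-way ANOVA and the Tukey-Kramer multiple comparison procedure", which "will be used to compare levels OSU_Senescence transcripts across the levels of categorical prognostic variables (e.g. stage of disease"). No covariate is mentioned. For quantitative factors it uses Pearson and Spearman correlations "to explore the strength of the relationship between" p16, the senescence transcripts and "quantitative prognostic factors (e.g., age"). Age thus appears only as one variable in pairwise correlations. The section adds: "Two-sided hypothesis tests of the correlations will be used", and "With such a small sample size, this is an exploratory aim".

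Elsewhere the protocol treats the panel as related to age. The biomarker table in section 4.12 reads "Molecular markers of aging: OSU_Senescence DNAge Inflammatory Cytokines". Section 7.2 says: "Levels of OSU_Senescence mRNA expression or DNAge values will be compared to an age-matched control dataset". That matching serves the comparison of patients with external controls. It does nothing for comparisons of patients with each other.

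**The concern.** Stage and the other prognostic factors in 7.3 are observed characteristics. Eligibility (section 3.3) sets a lower age limit of 60 and no upper limit, and it spans unresectable IIIA, IIIB and IV non-small cell disease and extensive-stage small cell disease. Nothing in the design makes ages comparable across these categories.

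Two things follow for a transcript that rises or falls with age. First, if the groups differ in age, the ANOVA attributes the resulting marker difference to stage, and the same problem affects a simple correlation with any quantitative factor that itself varies with age. Second, even where ages are similar, the variation due to age sits in the residual and blurs any real difference. At stake is the interpretation of the correlative results and the leads they give for later work.

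**Working it through.** **No figure to reproduce.** Section 7.3 states no sample size, alpha, effect size or power.

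**Does another section supply the age term?**
- Section 6.2 adjusts models for clinical and demographic variables, but those are the functional-status and resiliency models.
- Section 7.5 describes linear models with a contrast matrix and names no covariate.
- Section 7.1 lets details change as laboratory techniques develop; that is not a provision for confounding.
- The age matching in 7.2 concerns external controls only.

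None does.

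**Inputs.** N = 20 comes from section 3.1 (section 6.1 speaks of enrolling 30). The blood subset will be smaller than the number enrolled, since sections 4.12 and 7.2 exclude patients already on treatment; 12 serves as a low case. Assumed, because the documents are silent: two equal groups, alpha 0.05 two-sided, a linear age effect, within-group age-marker correlation rho of 0 to 0.7, and age gaps of 0.5 and 1 SD.

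**Bias.** With marker and age in within-group SD units and no stage effect, the expected false stage difference is rho × gap. For rho 0.5 and a one-SD gap this is 0.5 × 1 = 0.5 SD.

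**Rejection rate given a systematic gap.** For the one-way ANOVA with 10 v 10, the F statistic has 1 and 18 df and noncentrality (10 × 10 / 20) × (rho × gap)² = 5 × (rho × gap)². For rho 0.5 and a one-SD gap this is 5 × 0.25 = 1.25, which gives rejection in about 18.5%. Simulation (20,000 runs per cell, no stage effect) gives, for gaps of 0.5 SD / 1 SD:

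| rho | N=12 ANOVA | N=20 ANOVA | N=30 ANOVA |
|---|---|---|---|
| 0.3 | 5.7% / 7.4% | 6.1% / 9.9% | 6.9% / 12.6% |
| 0.5 | 7.1% / 12.5% | 8.3% / 18.7% | 10.5% / 26.2% |
| 0.7 | 8.7% / 19.4% | 11.5% / 32.2% | 15.1% / 45.9% |

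ANCOVA with age stays between 4.8% and 5.4% in every cell. The ANOVA rate rises with N, because the bias does not shrink as the sample grows.

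**How often does chance alone give such a gap?** With 10 v 10 the standard error of the age difference is √(2/10) = 0.447 SD. A gap of at least 0.5 SD is |Z| ≥ 0.5/0.447 = 1.12, about 26% of studies. A gap of at least 1 SD is |Z| ≥ 2.24, about 2.5%. When gaps arise only in this way, the unadjusted test rejects in about 5% of studies overall at every rho from 0 to 0.7.

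**Power with no systematic gap.** For a one-SD stage difference with 10 v 10, the ANOVA noncentrality is 5 × 1² = 5, giving power of about 56%. ANCOVA reduces the residual variance by the factor 1 − rho² (0.91, 0.75 and 0.51 at rho 0.3, 0.5 and 0.7) and loses one error df (17 left). By simulation with ages varying at random:

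| rho | ANOVA | ANCOVA |
|---|---|---|
| 0 | about 56% | about 53% |
| 0.3 | about 56% | about 58% |
| 0.5 | about 56% | about 66% |
| 0.7 | about 56% | about 82% |

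Repeat runs agree to within about a point. For a 1.2 SD difference, adjustment begins to pay at N=20 somewhere between rho 0.2 and 0.3. At N=12 and rho 0 the cost is about 4 points (46.4% to 42.1%).

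**The case against.** The best defence is that this is a declared exploratory aim in a single-arm feasibility pilot, that 7.3 looks at age in its own right, and that the section undertakes to compare levels, not to claim a stage effect. The panel has more than 70 transcripts, including T-cell subtype, exhaustion and housekeeping genes (section 7.2). For those unrelated to age, an age covariate gains nothing and costs some power.

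Much of this stands. It sets the severity and means the cost must be stated. It does not remove the point: the exploratory label is justified by small sample size, which speaks to imprecision, while confounding by age would persist in a larger sample. A separate correlation of each marker with age does not show whether a stage difference survives allowance for age.

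Three stronger readings are tempting, and the documents do not support them:

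- A reader might infer that the planned ANOVA has a false-positive rate of 8% to 32%. Those figures are conditional on a systematic age gap of the stated size at rho 0.5 to 0.7. The documents report no association between age and stage, and chance gaps leave the test at its 5% level. A one-SD gap by chance is rare with 10 v 10.
- A reader might infer that 7.3 itself expects the transcripts to correlate with age. It only proposes to explore that relationship. The support for an age link is the classification in 4.12 and the control matching in 7.2.
- A reader might infer that power is always lost without adjustment. That holds only for transcripts that track age well enough; near rho 0 the direction reverses.

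The ANOVA sentence also covers OSU_Senescence transcripts only, so the point does not extend to DNAge.

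**Conclusion.** The omission is real and no other section repairs it. For transcripts that track age, the 7.3 analyses cannot separate age from stage or another prognostic factor, and they are less sensitive than they could be. The size depends on two unknowns, rho and the age gap: it is negligible at rho 0.3 with a half-SD gap (about 6% rejection against a nominal 5%) and substantial at rho 0.7 with a one-SD gap (about 32%). The calculations cover two equal groups; no figure was computed for the correlations, where the argument is qualitative. Recruitment, adherence, retention and the functional-status analyses are unaffected. This is a minor point, worth making because the remedy is cheap.

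**What to change.** In section 7.3, for p16 and the OSU_Senescence transcripts:

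- Replace the one-way ANOVA with ANCOVA using age as a continuous covariate, with Tukey-Kramer comparisons on the age-adjusted means.
- For quantitative factors other than age, use partial Spearman correlations adjusted for age.
- Report the unadjusted results alongside as descriptive, so that readers can see what adjustment changes.

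Age is an eligibility criterion and so is known for every patient; no new data are needed. The cost is a change of wording, one error degree of freedom (with four stage groups and 20 patients, 20 − 4 − 1 = 15 remain) and, for transcripts unrelated to age, about 3 points of power at N=20 and about 4 at N=12.

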7.4 Obtaining Samples

Peripheral blood will be obtained by clinic staff for mRNA, DNA, and flow cytometric studies. Samples will be obtained in clinical space (currently on HTC and 5th floor James, or inpatient settings as examples). Specifically, approximately 40ml of peripheral blood will be collected into phlebotomy tubes: up to 20ml in purple top EDTA tubes and 20ml in serum separator tubes.

7.5 Sample processing

Sample pick up and processing will be performed in the Leukemia Tissue Bank using the following general procedure for cryopreservation of samples.

Plasma: To obtain the plasma the blood collected in EDTA coated tubes will be transferred to 50 ml sterile tube and centrifuged at 1800 rpm for 10min at room temperature. The supernatant (plasma) will be collected and stored at -80°C for further studies. The cellular pellet will be gently re-suspended in PBS to reach 2X the original volume (for 10ml of plasma 20ml PBS) and then stratified in 1X of Ficoll-Paque. This will be centrifuged at room temperature for 20 min at 2000 rpm. The white ring containing monocytes, T- and B- lymphocytes will be removed and washed with FBS enriched culture media. The tube will be centrifuged at 1200 rpm at room temperature for 6 min. The cellular pellet will be resuspended in 90% FBS and 10% DMSO and placed in cryo-tubes at -80°C and after 3 days will be placed in liquid nitrogen for long-term storage.

Serum/PBMCs: For the serum collection the tubes will be centrifuged at 2,200-2,500 rpm for 15 min and the serum will be stored at -80°C. PBMC: Blood samples will be diluted in an equal volume of phosphate buffered saline containing 2% fetal bovine serum (PBS/2%FBS). Diluted samples will be gently mixed and then carefully layered on top of Histopaque 1077 density medium (Sigma-Aldrich #10771) in a conical tube. The amount of density medium used will equal the original blood aliquot volume. Tubes will then be centrifuged at 1200xg for 20 minutes at room temperature with the centrifuge brake set to 'off'. Following separation, PBMCs will be removed from the gradient interface, placed into a fresh conical tube, washed in PBS/2%FBS solution, pelleted and then stored in cryopreservation medium.

T-cells: Whole blood collected in a purple top EDTA tube will be divided into two equal volume portions, approximately 5mL each. RosetteSep Human T Cell Enrichment Cocktail (Stem Cell Technologies # 15061) will be added to each tube at a ratio of 50uL per mL of whole blood. Tubes will be mixed by inversion and incubated for 20 minutes at room temperature. Next, samples will be diluted in an equal volume of phosphate buffered saline containing 2% fetal bovine serum (PBS/2%FBS). Diluted samples will be gently mixed and then carefully layered on top of Histopaque 1077 density medium (Sigma-Aldrich #10771) in a 50mL conical tube. The amount of density medium used will equal the original blood aliquot volume (~5mL). Tubes will then be centrifuged at 1200xg for 20 minutes at room temperature with the centrifuge brake set to 'off'. Following separation, enriched T-cells will be removed from the plasma interface using a pipette and placed into a fresh 15mL conical tube. The cells will be washed by adding PBS/2%FBS to the tubes until they are filled to the top fill line. Tubes will then be centrifuged at 400 x g for 4 minutes at room temperature with maximum brake. The resulting supernatant will be removed with a pipette and transferred to a 1.5 mL microcentrifuge tube. This sample will be centrifuged at 400 x g for 4 minutes at room temperature with maximum brake. The resulting supernatant will be carefully and completely removed using a pipette. The remaining T-cell pellet will be stored in a -80 ° freezer until processing.

DNA/RNA recovery and basic analyses: Under the supervision of [name], harvested cell mRNA will be converted to cDNA using the Promega ImProm-II Reverse Transcription System (Promega

#A3802) and random hexamer primers (Invitrogen #588875) as directed by the manufacturers. p16 levels will be measured using a Taqman-based quantitative RT-PCR methods essentially as described by Liu et al. (20). Validated Taqman-based controls for T-cell purity (CD3G, Applied Biosystems #4331182 Hs00962186), sample viability (p14ARF, Applied Biosystems #4351370 HUMP14-ARF3) and RNA quantity (YWHAZ, Applied Biosystems #4331182 Hs03044281) are included in this analysis. Data clean up: Data will be filtered to exclude relatively invariant features (IQR = 0.5) and features below the detection threshold (defined for each sample by a cutoff corresponding to approximately twice standard deviation of negative control probes plus the mean of them) in at least half of the samples. Basic analysis Using R/Bioconductor and the filtered dataset, linear models for microarray data analysis⁴⁷ will be employed with a contrast matrix for the comparisons. P values will be used to rank miRNAs and mRNA of interest, and correction for multiple comparisons will be done by the Benjamini-Hochberg method.⁴⁸

Assessment*:	Screen	Visit 1 (Baseline)	Every Treatment Visit	Visit 2 (4 weeks)	Visit 3 (7 weeks)	Visit 4 (10 weeks)	Visit 5 (13 Weeks) End of intervention	Visit 6 (24 weeks)	Follow up to 24 months (2 years)
Signed Informed Consent	x								
Inclusion/Exclusion	x								
Medical & Cancer History	x								
Sociodemographic		x							
Disease Assessments		x						x	
Physical Exam		x			x		x	x	
Vital Signs		x			x		x	x	
SPPB		x			x		x	x	
2-6 MWT		x			x		x	x	
PROMIS-10		x			x		x	x	
Blood Chemistry		x			x		x	x	
Biomarker Testing (blood and stool)		x			x		x	x	
Functional Status Assessments		x	x	x	x	x	x	x	
PROMIS-10		x		x	x	x	x	x	
GAD-7		x		x	x	x	x	x	
PHQ-9		x		x	x	x	x	x	
EORTCQLQ-30		x		x	x	x	x	x	
EORTC LC-13		x		x	x	x	x	x	
POMS-12		x	x	x	x	x	x	x	

Toxicities/ Disease Response		X		X	X	X	X	X	
Survival Status									X
Semi-structured interview							X		

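### The T-cell procedure in section 7.5 transfers the wash supernatant, not the pelleted cells, and then contradicts itself by storing a T-cell pellet; a minor wording correction is needed

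*Combined protocol and SAP*

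**What the plan says.** All the steps below are in the combined protocol and SAP, section 7.5 (Sample processing), under T-cells.

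- After density separation, "enriched T-cells will be removed from the plasma interface using a pipette and placed into a fresh 15mL conical tube".
- Wash: "The cells will be washed by adding PBS/2%FBS to the tubes until they are filled to the top fill line".
- First spin: "Tubes will then be centrifuged at 400 x g for 4 minutes at room temperature with maximum brake".
- Transfer: "The resulting supernatant will be removed with a pipette and transferred to a 1.5 mL microcentrifuge tube".
- Second spin: "This sample will be centrifuged at 400 x g for 4 minutes at room temperature with maximum brake".
- Removal: "The resulting supernatant will be carefully and completely removed using a pipette".
- Storage: "The remaining T-cell pellet will be stored in a -80 ° freezer until processing".

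No sentence says what happens to the pellet left in the 15 mL tube after the first spin.

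Section 7.5 also describes two other cell preparations, one in the plasma paragraph and one for PBMCs. Both keep the pelleted cells after washing. Section 7.1 states that the laboratory details may change and are guidelines only.

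**The concern.** A wash spin exists to bring the cells down so that the wash fluid can be thrown away. Here the fluid is carried forward and the cells are left behind without comment. The closing sentence nevertheless assumes that the T cells are in the small tube.

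What is at stake is the T-cell material for the correlative work. Section 7.2 says OSU_Senescence was built to characterise peripheral blood T lymphocytes, and it allots 10 mL of blood to T-cell isolation. Section 7.5 measures p16 by RT-PCR on harvested-cell mRNA, with a T-cell purity control. Section 7.3 then correlates p16 and the senescence transcripts with prognostic factors.

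The material is scarce. Under the footnote to Table 2 in section 4.12, patients already on treatment give no research blood, and a pre-treatment baseline sample cannot be drawn again once therapy has begun. The instructions run to catalogue numbers and brake settings, which invites staff to follow them as written.

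**Working it through.** The plan gives no figure to reproduce. The check is a trace of which fraction each step carries forward, followed by a comparison of tube volumes.

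**Trace, as written in section 7.5 (T-cells)**

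| Step | Fraction acted on | Where the sedimented T cells are afterwards |
|---|---|---|
| Cells placed in 15 mL tube and washed | Cell suspension | 15 mL tube, in suspension |
| First spin, 400 x g, 4 min | Whole tube | 15 mL tube, in the pellet |
| Transfer to 1.5 mL tube | Supernatant | Still in the 15 mL tube; not mentioned again |
| Second spin, 400 x g, 4 min | Transferred supernatant | Still in the 15 mL tube |
| Supernatant removed completely | Fluid in 1.5 mL tube | Still in the 15 mL tube |
| Pellet frozen | Residue in 1.5 mL tube | Still in the 15 mL tube |

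Only cells that failed to sediment in the first spin can reach the stored tube. The second spin has the same force and duration as the first, and the plan relies on it to produce a T-cell pellet. It cannot consistently rely on those settings to pellet T cells in the second tube while assuming that they leave the cells in suspension in the first.

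**Volumes**

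- Receiving tube: 1.5 mL (section 7.5).
- Wash tube: a 15 mL conical tube filled to its top line. The plan does not state the volume at that line. I assume 14 to 15 mL from the nominal size.
- Ratio: 14 / 1.5 = 9.3 and 15 / 1.5 = 10.

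The supernatant is therefore roughly nine to ten times what the receiving tube can hold, so the transfer as worded cannot be completed. A pellet resuspended in a small volume would fit.

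**Comparison within section 7.5**

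| Preparation | Kept after the wash |
|---|---|
| Plasma paragraph (mononuclear ring) | Pellet, resuspended in freezing medium |
| PBMCs | Pelleted cells, stored in cryopreservation medium |
| T-cells | Supernatant is transferred; pellet not mentioned |

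The closing sentence, the tube sizes and the two parallel procedures all point the same way. The transfer sentence has most likely lost the words that discard the supernatant and resuspend the pellet.

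**What depends on this material**

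- p16 by RT-PCR (section 7.5) and OSU_Senescence measured in T cells (section 7.2) depend on it most directly.
- Section 7.2 allows RNA and DNA to come from purified T cells or from PBMCs, and allows DNAge to use either or both. PBMCs come from a separate 10 mL. OSU_Senescence and DNAge therefore have a second source.
- The adherence component of the primary endpoint (section 6.1) counts collection of specimens, not assay yield. The rule of 13 of 20 patients continuing (section 6.2.1) does not involve specimens at all.

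**The case against.** The strongest reply is that no competent laboratory would do what the sentence says. The end product is named, the literal transfer does not fit the tube, and the neighbouring procedures keep the cells. Section 7.1 calls the details guidelines, and section 7.5 introduces its steps as a general procedure carried out by a tissue bank, whose own working procedure is not among the documents. Much of this stands. It makes a drafting slip far more likely than a real loss of samples. It does not make the sentence right: section 7.1 allows for changes as techniques develop, which is different from an instruction that defeats its own purpose.

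A reader might go further and infer any of the following. The documents do not support them.

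- *The stored tubes will hold few or no T cells.* This follows only if the text is carried out literally, and nothing shows that it was or will be.
- *About 10% of the cells are carried forward.* The ratio 1.5 / 15 = 10% compares tube volumes. The plan gives no T-cell recovery figure.
- *The senescence markers could not be derived.* The PBMC route in section 7.2 remains for OSU_Senescence and DNAge, although PBMCs are not purified T cells and do not replace a T-cell-specific measurement.
- *Depleted samples would fall below the detection threshold in section 7.5.* That rule filters out features that are undetected in at least half of the samples. It sets no minimum input for a sample.

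Section 7.5 also includes controls for T-cell purity (CD3G) and RNA quantity (YWHAZ). They would probably reveal an empty tube, but only after the blood had been processed.

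**Conclusion.** The contradiction is real and can be seen on the page: section 7.5 moves the supernatant to the 1.5 mL tube and then stores a T-cell pellet from it. If followed literally, the T cells that sedimented in the wash spin would not be in the stored sample. How many cells that would be cannot be calculated from the documents.

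The reach is limited. T-cell-specific measures, chiefly p16 and T-cell OSU_Senescence, are exposed in patients who give research blood. Section 7.2 schedules OSU_Senescence at two visits. Section 7.3 describes the aim as exploratory because of the small sample. The primary feasibility endpoint is untouched.

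This is a minor correction to an exploratory laboratory procedure. The conclusion rests on two assumptions: that the wash spin pellets T cells, as the plan itself assumes for the identical second spin, and that the 15 mL tube holds close to its nominal volume at the top line. The contradiction between the sentences does not depend on the second assumption.

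**What to change.** In section 7.5 (T-cells), reword the transfer sentence so that the wash supernatant is removed and discarded, and the T-cell pellet is resuspended in a small volume and transferred to the 1.5 mL tube. The plan gives no resuspension volume, so take it from the processing laboratory's working procedure. Keep the second spin, the removal of its supernatant and the storage step as written.

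Ask the laboratory to confirm in writing which procedure was used for any T-cell samples already stored. If the literal text was followed for any of them, identify those samples before the p16 and T-cell OSU_Senescence results are analysed.

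The cost is one sentence and one laboratory check. It adds no blood draw, patient burden or change to the analysis.
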